2.3 STUDY DESIGN

Study SNDX-275-0603 is a randomized, placebo-controlled, double-blind, multicenter Phase 1b/2 study evaluating the combination of entinostat with avelumab in patients with advanced epithelial ovarian cancer. The study has 2 phases: an open-label Safety Lead-in (Phase 1b) followed by an Expansion Phase (Phase 2) (Figure 2-1).

A cycle is defined as 14 days in length. During treatment, patients will attend study center visits for study evaluations on Days 1 and 8 of Cycles 1 and 2, and on Day 1 of each cycle thereafter. Patients will have radiological disease assessments performed within 28 days prior to enrollment, then every 6 weeks (\pm 3 days) when measured from Cycle 1, Day 1, during study treatment through Week 36 (i.e., Weeks 6, 12, 18, 24, 30, 36) until unequivocal PD per RECIST 1.1. Patients remaining on study after Week 36 will undergo radiological disease assessments every 8 weeks (\pm 3 days) until unequivocal PD occurs. Disease will be assessed by computed tomography (CT) and magnetic resonance imaging (MRI), as appropriate, using the same method used for the screening evaluation, and response will be assessed by the investigator using RECIST 1.1 and irRECIST. Collection of fresh tumor tissue core biopsy (image-guided if applicable) and blood samples are outlined in Section 6.1 of the protocol.

Figure 2-1. Study Schema

Patients will remain on study treatment until unequivocal PD, intolerable toxicity, or one of the other study withdrawal criteria is met (see Protocol Section 11). Patients

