All patients are to be followed for disease progression according to the protocol-specified schedule even after a non-protocol, anti-cancer therapy is started. For the primary analysis of PFS, documented disease progression (or death without prior disease progression) occurring after the start of such therapy will be considered as a PFS event.

Table 3-1. Date of Progression or Censoring for Progression-free Survival

Situation	Date of Progression or Censoring	Outcome
Documented disease progression	Date of disease assessment showing documented disease progression	Progressed
Death without documented progression	Date of death	Progressed
No baseline disease assessments	Date of randomization	Censored
No post-baseline assessment and no death	Date of randomization	Censored
Death or documented progression after more than one missed consecutive post-baseline disease assessment	Date of last disease assessment visit without documentation of disease progression that is before the missed visit or date of randomization, whichever is later	Censored
Alive and without documentation of disease progression	Date of last disease assessment	Censored
Patient lost to follow-up (or withdrew consent from study participation) before documented	Date of last disease assessment	Censored

progression or death		
----------------------	--	--

Sensitivity Analyses of Progression-free Survival

Sensitivity analyses will be undertaken for calculation of the primary endpoint in order to evaluate the robustness of the analysis by changing one or more of the censoring rules stated in the primary analysis ([Table 3-1](#)). The following sensitivity analyses will be performed for PFS:

Progression-free Survival Sensitivity Analysis 1 (forward-dating PFS assessment time)

A main source of potential bias for the PFS endpoint arises from differences between the actual and observed date of disease progression, particularly if the difference is systematically related to the patient's treatment arm. Deviations from scheduled assessment times may be due to 1) AEs causing delays on one treatment arm, 2) more frequent assessments in one treatment arm because of toxicity or worsening symptoms, 3) delay in assessments because patients are doing well.

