Objective response rate will be estimated based on the crude proportion of patients in each treatment arm whose best overall response during the course of study treatment is CR or PR. Tumor response will be assessed using RECIST 1.1 and irRECIST, as outlined in Protocol Section 5.1. Approximate 95% confidence intervals (CIs) will be calculated by treatment arm for the true ORR. The inferential comparison of the observed ORRs will be made using the Cochran-Mantel-Haenszel chi-square test, stratified by the randomization stratification factor(s). The corresponding results without stratification will be reported as supplemental analyses.

Duration of Response and Time to Response

Duration of response will be calculated for patients who achieve CR or PR. For such patients, DOR is defined as the number of months from the start date of the PR or CR (whichever response occurs first and subsequently confirmed), to the first date that recurrent disease or PD is documented. The same analysis will be repeated for patients who achieve immune-related CR (irCR) or immune-related PR (irPR). The date of progression or censoring for DOR will be determined according to the conventions listed [Table 3-5](#). These conventions are based on the May 2007 FDA Guidance for Industry, ‘*Clinical Trial Endpoints for the Approval of Cancer Drugs and Biologics*’. DOR will be summarized descriptively using the Kaplan-Meier method.

Table 3-5. Date of Progression or Censoring for Duration of Response

Situation	Date of Progression or Censoring	Outcome
Documented disease progression	Date of disease assessment showing documented disease progression	Progressed
Death without documented progression	Date of death	Progressed
Death or progression after more than one missed disease assessment	Date of last disease assessment visit without documentation of disease progression that is before the missed visit	Censored
Alive and without documentation of disease progression	Date of last disease assessment	Censored

Time to response will be calculated for patients who achieve a CR or PR. For such patients, TTR is defined as the number of months from the randomization date to the first date the patient achieved a PR or CR (whichever response occurs first and was subsequently confirmed). The same analysis will be repeated for patients who achieve irCR or irPR.

Clinical Benefit Rate

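### Table 3-5 leaves out "consecutive" from the missed-assessment rule, so two scattered missed scans censor a progression or death for DOR that counts as a PFS event (minor)

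*SAP*

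**What the plan says.** SAP Section 3.8 gives separate event and censoring tables for PFS and DOR.

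- **PFS (Table 3-1, repeated in Tables 3-2 to 3-4).** The missed-scan row applies to "Death or documented progression after more than one missed consecutive post-baseline disease assessment". The censoring date is the last progression-free assessment "that is before the missed visit or date of randomization, whichever is later".
- **DOR (Table 3-5).** The matching row applies to "Death or progression after more than one missed disease assessment". The censoring date is "Date of last disease assessment visit without documentation of disease progression that is before the missed visit", with no earliest permitted date.
- **Reason given.** Of the DOR rules the SAP says "These conventions are based on the May 2007 FDA Guidance for Industry". It does not say why DOR should differ from PFS.
- **Reach.** The Clinical Benefit Rate paragraph says that duration of clinical benefit follows the DOR method.
- **Calendar (Section 2.3).** Scans are six-weekly "during study treatment through Week 36 (i.e., Weeks 6, 12, 18, 24, 30, 36"), and then: "Patients remaining on study after Week 36 will undergo radiological disease assessments every 8 weeks".

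**The concern.** PFS and DOR are read from the same scans and end at the same progression. For a responder they should differ only in the starting point: randomization for one, first response for the other. The missing word breaks that link. Under the PFS rule, one long gap in imaging makes the progression date unreliable, and the patient is censored. Under the literal DOR rule, two isolated misses months apart have the same effect, even with clean scans between them and a well-dated progression.

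Two things are at stake. The same patient can have a PFS event and a censored DOR with no stated reason. In addition, the chance of collecting two isolated misses rises with the number of scans, so the rule removes events mainly from the longer responders, and the censoring is then related to the outcome.

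**Working it through.** No figure in the SAP depends on this rule, so there is none to reproduce. The check is one worked patient, an exact count, and a simulation on the SAP calendar.

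**1. One patient.** Assume randomization and Cycle 1 Day 1 coincide. Response is at Week 6, confirmed at Week 12. Week 18 is missed, Week 24 shows continued response, Week 30 is missed, and PD is seen at Week 36. One month is 30.4375 days (Section 3.8).

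- PFS, Table 3-1: no two misses are adjacent, so this is an event at 36 × 7 / 30.4375 = 8.3 months.
- DOR, Table 3-5 as written: two misses, so censored. The last progression-free scan before the missed visit is Week 24 if the second miss is meant, giving 18 × 7 / 30.4375 = 4.1 months. It is Week 12 if the first is meant, giving 6 × 7 / 30.4375 = 1.4 months.
- DOR with the word restored: event at (36 − 6) × 7 / 30.4375 = 6.9 months, in line with PFS.

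**2. Exact count of patients on whom the two rules disagree.** Let *k* be the scheduled scans that could be missed before the PD scan, and *q* the miss probability per scan. The SAP gives no miss rate, so *q* is an assumption, as is independence between scans. There are C(k − j + 1, j) ways to place *j* misses with no two adjacent. The share with at least two misses and no adjacent pair is therefore

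Σ (j ≥ 2) C(k − j + 1, j) × q^j × (1 − q)^(k − j).

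For k = 8 and q = 0.10: 21 × 0.01 × 0.5314 + 20 × 0.001 × 0.5905 + 5 × 0.0001 × 0.6561 = 0.1116 + 0.0118 + 0.0003 = 12.4%.

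| Scans before PD (PD week if counted from Week 18) | q = 2% | q = 5% | q = 10% | q = 20% |
|---|---|---|---|---|
| 4 (Week 44) | 0.1% | 0.7% | 2.4% | 7.7% |
| 6 (Week 60) | 0.4% | 2.1% | 6.9% | 18.0% |
| 8 (Week 76) | 0.8% | 4.1% | 12.4% | 27.6% |

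The excess grows with time in response. The last row needs PD at 76 × 7 / 30.4375 = 17.5 months, which many patients cannot reach before the cutoff.

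**3. Size at the planned analysis.** Section 2.3.1 plans about 12 months of accrual plus 12 of follow-up. Section 3.8 cuts the data at the 97th PFS event. I took follow-up as uniform over 12 to 24 months (assumption). Other assumptions: response at Week 6, Week 12 confirmation scan attended, exponential time from response to PD with median 26, 39 or 52 weeks, independent misses, and PD recorded at the first attended scan at or after progression. Both tables are read equally literally, so Table 3-1 counts any consecutive pair before PD.

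| Share of observed PDs censored | q = 5% | q = 10% |
|---|---|---|
| Table 3-5 as written | about 2% | 6–8% |
| Table 3-1 | about 1% | 3–4% |
| Excess from the missing word | about 1 point | about 3–4 points |

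If every responder were instead followed to PD with no cutoff, the Table 3-5 shares would be 4–11% and 12–25%.

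**The case against.** The best defence is that Table 3-5 was meant to say what Table 3-1 says. Its censoring date refers to a single missed visit, which fits one gap better than scattered misses, and a programmer might supply the missing word. That is a plausible guess at intent. But the qualifier stands in all four PFS tables and is absent only here, and a programmer who follows Table 3-5 exactly gets the other result.

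The defence is right that the stakes are low. DOR is secondary, confined to responders and summarized by Kaplan–Meier without a test.

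Several stronger readings are tempting, and the document does not support them:

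- **That any two missed scans make DOR and PFS disagree.** After two consecutive misses both tables censor. Only patients with two or more misses and no adjacent pair are treated differently.
- **That the rule removes a large share of events.** The no-cutoff shares above suggest this, but they ignore the planned cutoff.
- **That it shortens median DOR.** With the cutoff, censoring before the first miss moved the Kaplan–Meier median in none of the six scenarios. Censoring before the second miss moved it in one, upward. No direction can be claimed.
- **That the singular missed visit is a separate fault of Table 3-5.** Table 3-1 uses the same phrase. It becomes ambiguous in Table 3-5 because misses there need not form one gap.
- **That text and table conflict over death.** The DOR text runs "to the first date that recurrent disease or PD is documented" and omits death, but it then refers the reader to Table 3-5, which has an explicit row making death an event. The table governs.

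**Conclusion.** The point holds as an error of wording, with minor effect. Read literally, Table 3-5 censors an observed progression or death for DOR in a responder with two or more missed scans and no consecutive pair, although the same event counts for PFS. Duration of clinical benefit inherits the rule.

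The absence of the word is certain. The size is not, because it rests on assumed miss rates, independence between scans, exponential response durations and uniform 12 to 24 months of follow-up. Correlated misses, or a different cutoff in practice, would change the figures. On these assumptions the missing word adds about 1 percentage point to the share of observed progressions censored at a 5% miss rate, and about 3–4 points at 10%. The primary PFS test, its alpha and the 97-event target are untouched.

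**What to change.** In Table 3-5, change the row to cover death or *documented* progression after more than one missed *consecutive* disease assessment. Set the censoring date to the last progression-free assessment before those consecutive missed visits, and no earlier than the response date. The earliest date is needed because the row is not limited to scans after response onset, so a miss before the response could otherwise place the censoring date before DOR begins. If a different rule for DOR is intended, say so, give the reason, and state which missed visit sets the censoring date.

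Optionally, add death from any cause to the DOR definition in the text so that it reads the same as the table.

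The cost is SAP wording, with the DOR and duration-of-clinical-benefit programming specifications aligned to it. No data collection, sample size or primary analysis changes.

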2.1.2 Secondary Objectives

Efficacy: To evaluate the efficacy of entinostat in combination with avelumab in patients advanced epithelial ovarian cancer, as determined by:

- PFS based on immune response RECIST (irRECIST)
- Overall response rate (ORR) (i.e., complete response [CR] or partial response [PR]) based on RECIST 1.1 and irRECIST
- Clinical benefit rate (CBR) (i.e., CR, PR, or stable disease [SD] for at least 24 weeks) based on RECIST 1.1 and irRECIST
- Overall survival (OS)

In patients with best overall confirmed response of CR or PR:

- Duration of response (DOR)
- Time to response (TTR)

Pharmacokinetics: To assess the effect of entinostat on the pharmacokinetics (PK) of avelumab

Safety: To evaluate safety and tolerability of entinostat in combination with avelumab, as measured by adverse events (AEs) and clinical laboratory parameters

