2.2.2 Secondary Endpoints (analyzed for the same populations as the primary endpoint)

- PFS by irRECIST
- ORR (CR or PR) by RECIST 1.1 and irRECIST
- CBR (CR, PR, or SD for at least 24 weeks) by RECIST 1.1 and irRECIST
- OS
- DOR and TTR (in patients who experience best overall response of CR or PR)
- The effect of entinostat on the PK of avelumab

Safety:

- Determination of DLTs, MTD, and RP2D
- Incidence of treatment-emergent adverse events (TEAEs), serious adverse events (SAEs), AEs resulting in the permanent discontinuation of study drug, and deaths occurring within 30 days of the last dose of study drug
- Changes from baseline in laboratory, vital signs, Eastern Cooperative Oncology Group (ECOG), physical examination, and electrocardiogram (ECG) values

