3.8 Efficacy Analysis

Efficacy analyses will be performed using the FAS and, where appropriate, the Per-Protocol Set. The efficacy outcomes for the patients enrolled in the Phase 1b portion of the study will be reported in listing format and may be summarized in a descriptive manner using the analysis conventions described below, as appropriate. The primary analysis of PFS will be based on the first 97 PFS failures. The calendar date of the 97th event will serve as the data cutoff date for the primary analysis. The primary analysis of the secondary endpoints, exploratory endpoints, and safety will occur at the time of the primary PFS analysis. An interim analysis is planned after 65 PFS failures (67% of total events) observed in Phase 2. The calendar date of the 65th event will serve as the data cutoff date for the interim analysis. With the exception of PFS, all hypothesis testing will be assessed using a one-sided significance level of 0.1. The Lan-DeMets alpha spending function with an O'Brien-Fleming type boundary will be used to control type I error for multiple testing of PFS. The details of alpha spending are described in [Section 2.3.2](#).

Progression-free Survival

The primary efficacy endpoint is duration of PFS, defined as the number of months from randomization to PD or death due to any cause, whichever occurs first. Disease assessments will continue until PD, even after the originally assigned study treatment is discontinued. For purposes of analysis, 1 month is considered 30.4375 days. The duration of PFS as determined by RECIST 1.1 ([Eisenhauer 2009](#)) and irRECIST ([Seymour 2017](#)) will be summarized descriptively using the Kaplan-Meier method

(Kaplan 1958). Inferential comparisons between treatment arms will be made using the log rank test, stratifying on the randomization stratification factors. The Cox proportional hazard model (Cox 1972) with treatment as a factor, stratified by the stratification factors used in randomization, will be used to estimate the HR for treatment effect and corresponding 95% CI, without any other covariate adjustment. The corresponding results without stratification will be reported as supplemental analyses. The adequacy of the Cox model will be evaluated, including an assessment of the proportional hazards assumption (Therneau 2000).

For the interim and primary analyses, the date of progression or censoring for PFS will be determined according to the conventions listed in [Table 3-1](#).

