Clinical benefit rate, as determined by RECIST 1.1, will be estimated based on the crude proportion of patients in each treatment arm whose best overall response during the course of study treatment is a CR, PR, or SD lasting for at least 6 months. Stable

disease will be measured from the start date of study treatment until the criteria for PD is first met. The analysis of CBR and its duration will be based on the methods described above for ORR and DOR, respectively. Approximate 95% CIs will be calculated by treatment arm for the CBR. The comparison of the observed CBRs will be made using the Cochran-Mantel-Haenszel chi-square test, stratified by the randomization stratification factor(s). The corresponding results without stratification will be reported as supplemental analyses. Clinical benefit rate, as determined by irRECIST, will be estimated based on the crude proportion of patients in each treatment arm whose best overall response during the course of study treatment is an irCR, irPR, or irSD, lasting for at least 6 months. The analysis of CBR, based on irRECIST, will follow the same method described above.

Overall Survival

Overall survival is defined as the number of months from randomization to the date of death (due to any cause). Patients who are alive or lost to follow-up (as of the data analysis cutoff date) will be right-censored. The censoring date will be determined from the patients' date of last contact or data analysis cutoff date, whichever date occurs first. The analysis of OS will be based on the methods described above for PFS. The duration of OS will be summarized descriptively using the Kaplan-Meier method with 95% CIs, calculated using Greenwood's formula. For the primary analysis of OS, the difference in treatment effect will be tested using the stratified log rank test, stratifying on the randomization stratification factors. Estimation of the HR for treatment effect and its corresponding 95% CI will be determined using a stratified Cox proportional hazards model, without any other covariate. Homogeneity in the HRs across randomization strata will be examined by Wald's test using a two-sided significance level of 0.05.

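### Clinical benefit rate is defined with stable disease for at least 24 weeks in Sections 2.1.2, 2.2.2 and 3.3.1 but computed with at least 6 months in Section 3.8, and nothing reconciles the two

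*SAP*

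**What the plan says.** Three places in the SAP give the 24-week definition. Section 2.1.2 sets the secondary objective with stable disease (SD) "for at least 24 weeks) based on RECIST 1.1 and irRECIST". Section 2.2.2 lists the endpoint as "CBR (CR, PR, or SD for at least 24 weeks) by RECIST 1.1 and irRECIST", and Section 3.3.1 lists the efficacy variable in the same terms.

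Section 3.8, under Clinical Benefit Rate, says how the rate is computed. For RECIST 1.1 it takes the crude proportion of patients whose best overall response "is a CR, PR, or SD lasting for at least 6 months". For irRECIST the best response "is an irCR, irPR, or irSD, lasting for at least 6 months". The clock is also fixed there: stable "disease will be measured from the start date of study treatment until the criteria for PD is first met".

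Earlier in Section 3.8, in the PFS paragraph, the SAP sets the conversion used for analysis: "1 month is considered 30.4375 days". Section 2.3 schedules scans at Weeks 6, 12, 18, 24, 30 and 36 from Cycle 1 Day 1, each within 3 days either side.

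**The concern.** The objective, the endpoint list and the variable list carry one SD duration, and the section a programmer will follow carries another. No sentence equates the two or says which prevails. Section 3.8 followed as written would report a rate that is not the stated secondary endpoint, under both response criteria. CBR is compared between arms by a stratified Cochran-Mantel-Haenszel test and has its own tables (14.3.8A and 14.3.8B), so the mismatch would carry into a reported comparison.

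The gap also takes in part of a scheduled assessment. The Week 24 scan sits at the 24-week threshold and before the 6-month one, so the patients affected can be identified in advance.

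**Working it through.** The SAP states no figure that depends on the CBR threshold, so there is none to reproduce. The check is a unit conversion set against the scan schedule, followed by an illustration of size.

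**Thresholds**
- 24 weeks: 24 × 7 = 168 days (168 / 30.4375 = 5.52 months).
- 6 months: 6 × 30.4375 = 182.625 days (182.625 / 7 = 26.09 weeks).
- Gap: 182.625 − 168 = 14.625 days.
- The two would agree only with a month of 168 / 6 = 28 days, which is not the SAP's convention.

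**Against the scan schedule**
- Week 24 scan: 168 ± 3, days 165 to 171. Week 30 scan: 210 ± 3, days 207 to 213.
- SD with progression (PD) found at Week 24 on days 165 to 167: fails both rules.
- SD with PD found at Week 24 on days 168 to 171, or otherwise first met up to day 182: meets 24 weeks, fails 6 months.
- SD with PD found at Week 30: meets both rules.

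**Size, RECIST 1.1 only**

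Inputs from Section 2.3.1: 40 placebo and 80 entinostat patients; median PFS 4 vs 7 months, or 3 vs 5.25 months. Assumptions: exponential PFS, S(t) = exp(−ln 2 × t / median), with treatment start taken as the randomization date. Responders and deaths are not removed.

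*(a) Continuous PFS times, S(168) − S(182.625):*

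| Medians | Placebo | Entinostat | Patients |
|---|---|---|---|
| 4 vs 7 | 0.0307 | 0.0269 | 40 × 0.0307 + 80 × 0.0269 = 3.4 |
| 3 vs 5.25 | 0.0294 | 0.0297 | 40 × 0.0294 + 80 × 0.0297 = 3.5 |

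*(b) PD found only at scheduled scans.* Failures first seen at Week 24 are S(126) − S(168). If scans spread evenly over the seven-day window, 4 of the 7 days (168 to 171) fall in the gap:

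| Medians | Placebo | Entinostat | First seen at Week 24 | × 4/7 |
|---|---|---|---|---|
| 4 vs 7 | 0.1038 | 0.0848 | 4.15 + 6.78 = 10.9 | 6.2 |
| 3 vs 5.25 | 0.1049 | 0.0964 | 4.20 + 7.71 = 11.9 | 6.8 |

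Per arm (placebo, entinostat), (b) is 5.9 and 4.8 points at 4 vs 7 months, and 6.0 and 5.5 points at 3 vs 5.25 months. With the same scan timing in both arms, the between-arm difference moves 5.93 − 4.84 = 1.1 points or 5.99 − 5.51 = 0.5 points. Under (a) it moves less: 3.07 − 2.69 = 0.4 points, and almost nothing at 3 vs 5.25 months.

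**The case against.** The best defence is that 6 months is loose shorthand for 24 weeks, that the month convention stands in the PFS paragraph, and that little turns on the difference. The shorthand reading does not survive programming: the convention is worded for analysis in general, and only a 28-day month would make the two agree. The point about size largely stands. CBR is one of several secondary endpoints, no design figure rests on it, and a patient who is stable at Week 24 and progresses at Week 30 passes either rule.

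The counts above also lean high. A responder's class does not change under RECIST 1.1. Deaths are dated at death and not at a scan. Section 3.8 limits best response to the course of study treatment, and no allowance is made for patients already off it. The even spread of scan days is an assumption.

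Four stronger readings are tempting, and the document does not support them.

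- **Much larger effects.** A reader might take all 10.9 to 11.9 patients first seen at Week 24. With every Week 24 scan on or after day 168 in one arm and before it in the other, the between-arm shift would be 8.5 to 10.5 points. Those figures chiefly show how sensitive a 168-day cut is to the scan day, since PD at any in-window Week 24 scan fails the 6-month rule. Section 3.8 allows that delays may differ by arm, but nothing suggests so complete a split in a double-blind trial with scans fixed to the calendar.
- **Two competing rates.** Only Section 3.8 gives a computing rule, and one CBR table is listed per criterion. The practical risk is one reported rate that does not match its definition.
- **Censored stable disease as further evidence.** Section 3.8 says "The analysis of CBR and its duration will be based on the methods described above for ORR and DOR, respectively", and Table 3-5 gives censoring dates without saying whether censored SD that reaches the threshold counts. That detail would be open under a single threshold too, so it is a separate matter and does not support this contradiction.
- **A matching irRECIST count.** Progression there is confirmed by a repeat scan at least 4 weeks later, so the RECIST 1.1 figures do not carry over.

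**Conclusion.** The contradiction holds for both RECIST 1.1 and irRECIST, and it does not depend on any modelling. Its likely size is modest: roughly 3 to 7 of 120 patients under RECIST 1.1, and about 0.5 to 1.1 points between arms when PD is found at scheduled scans with similar timing in each arm. These figures rest on exponential PFS at the SAP's medians and, at the upper end, on an even spread of scan days. The number of SD patients who actually change class should be smaller. The matter should be corrected because a tested secondary endpoint must be computed as it is defined. It gives no ground to doubt the primary PFS analysis, its power or its alpha.

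**What to change.** Before unblinding, use one SD duration in Sections 2.1.2, 2.2.2, 3.3.1 and 3.8.

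- In both CBR sentences of Section 3.8, replace the 6-month duration with the endpoint definition of at least 24 weeks from the start of study treatment, applied to SD and irSD. Check first that the protocol, which is not at hand, says the same.
- State the threshold in days, and say how the ±3-day window around Week 24 is handled, for example by assigning an in-window scan to its scheduled week. A bare 168-day cut falls inside the window (days 165 to 171), so class would turn on whether the scan fell on day 167 or day 168.

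The cost is SAP wording and the matching derivation in the analysis dataset specification. No new data are needed. If the protocol turns out not to say 24 weeks, the two documents must be reconciled first.
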